**Table 2. Constructs and Measures (How data will be used, research aim, and time of administration)**

| Construct                            | Measure   | Use     | # items | Aim 2  |    | Aim 3 |    | Aim 2 / 3 |
|--------------------------------------|---|---------|---------|--------|----|-------|----|-----------|
|                                      |   |         |         | Screen | BL | BL    | 3M | Post      |
| Demographics                  | Age, Ethnicity, Race, Marital status, Education, Employment, SES, Living Arrangements, Gender/Gender Identity, Reason for visit, Health Insurance   | D, M    | 13      | x      |    | x     | x  |           |
| Alcohol Use                   | Heavy drinking frequency/quantity   | S, F, O | 2       | x      | x  | x     | x  |           |
|                                      | Drinks/week, quantity/frequency, maximum quantity   | F, O    | 4       |        | x  | x     | x  |           |
|                                      | Alcohol quantity before sex   | F, O    | 2       |        | x  | x     | x  |           |
| Alcohol problems              | SIP-2R  | F, O    | 26      |        | x  | x     | x  |           |
| Alcohol Protective Strategies | Positive alcohol behavioral strategies, Consumption self-control, Stopping/Limit setting, Harm reduction  | F       | 22      |        | x  | x     | x  |           |
| Sexual behavior               | Sex risk: (a) sex >1 partner, (b) sex with someone who had other partners, (c) did not use a condom every time                                      | S       | 7       | x      |    |       |    |           |
|                                      | Pregnancy attitudes and intentions  | D       | 9       |        | x  | x     | x  |           |
|                                      | Sex History: Lifetime partner #, Past 3 months partner #, Condom Use past 3 months, alcohol with sex past 3 months, # HIV-positive partners         | D, O    | 13      |        | x  | x     | x  |           |
|                                      | Partners: (a) #, (b) relationship type(s), (c) condom use, (d) involving alcohol, (e) partner STI testing, (f) monogamy, (g) trust, (h) risk of STI | D, F, O | 7xP     |        | x  | x     | x  |           |
|                                      | Sex-Related Alcohol Expectancies  | M       | 13      |        |    | x     | x  |           |

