| STI                           | Chart abstraction of sexually transmitted infection   | D, O    | 1       |        |    | x     | x  |           |
|                                      | Self-report History, Testing frequency and results  | D, O    | 7       |        | x  | x     | x  |           |
|                                      | Sexual Risk Reduction Strategies  | F       | 10      |        | x  | x     | x  |           |
| Information                   | HIV and STD Knowledge Questionnaires  | O, M    | 18      |        |    | x     | x  |           |
| Norms                         | Descriptive norms for women's number of partners, condom use, partner concurrency, binge drinking   | O, M    | 6       |        |    | x     | x  |           |
|                                      | Subjective norms for binge drinking, motivation to comply, condom use, multiple partners  | O, M    | 12      |        |    | x     | x  |           |
| Attitudes                     | Attitude toward heavy drinking  | O, M    | 5       |        |    | x     | x  |           |
|                                      | Attitudes toward partner concurrency scale  | O, M    | 10      |        |    | x     | x  |           |
|                                      | Health Values   | F       | 5       |        | x  | x     | x  |           |
|                                      | Relationship Values   | F       | 23      |        | x  | x     | x  |           |
|                                      | Condom Attitudes  | M       | 26      |        |    | x     | x  |           |
| Self-efficacy                 | Self-efficacy for drink refusal (DRSEQ-R10)   | O, M    | 10      |        |    | x     | x  |           |
|                                      | Self-efficacy for condom use for each partner   | O, M    | 3xP     |        |    | x     | x  |           |
| Condom Usage                  | Assessment of Correct Condom Use  | F, O, M | 10      |        | x  | x     | x  |           |
|                                      | Condom Influence Strategy Questionnaire   | F, O, M | 8       |        | x  | x     | x  |           |
| Behavioral Intentions         | Condom use for each partner   | O       | 1xP     |        | x  | x     | x  |           |
|                                      | Multiple partners   | O       | 1       |        | x  | x     | x  |           |

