Potential **mediators** include IMB constructs: (a) information, (b) motivation, and (c) skills. To assess information we will use knowledge questionnaires. To assess motivation, we will use measures of norms, attitudes, and behavioral intentions towards alcohol use, condom use, and partner concurrency. Importantly, we will assess condom use norms and intentions by partner type; we will also assess norms, attitudes and intentions towards partner concurrency, rarely done in prior intervention studies. To assess behavioral skills for condom use we will use a measure of condom use problems and assess self-efficacy by partner.

Potential **moderators** include demographic (e.g., age, race); sexual history (e.g., number of partners, STI diagnoses, prior victimization); mental health (depression and anxiety; assessed with PHQ-9 and GAD-7); drug use (DHQ).

**f. Intervention.** Women randomized to the **control condition** will receive (after the baseline CASI) a Fact Sheet on Alcohol Use and Risks to Women’s Health prepared by the CDC. This details gender differences in alcohol intoxication, facts about alcohol use and reproductive health, pregnancy, and other women’s health concerns. Control women will then be scheduled for their follow-up session.

Women randomized to the **BI** will receive a ~45 min BI (as detailed in Table 1 and Aim 2) delivered by a health educator. After the BI, participants will be told that they will receive daily mobile messages with health facts of the day for 3 months. Women will be encouraged to visit and use the website. At the end of the BI session, women will complete a post-BI satisfaction survey, be scheduled for the follow-up. For all women, at the end of the session, the RA will thank the participant and reimburse her \$30 for completing the CASI.

**g. Process measures.** We will assess the **fidelity** with which health educators implement the **BI** by reviewing session content against a content checklist based on the manual that to obtain a % adherence score; and using blind ratings that identify behaviors consistent with MI spirit (e.g., empathetic engagement,

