To determine **feasibility** of the BI and of an RCT, we will calculate the percentage of individuals who were: eligible; consented; attended their intervention; accessed the website; and returned for the follow-up. Based on previous research, we expect  $\geq 90\%$  of those assigned to a BI to attend their intervention. Based on our recent trials (R01-MH068171), we expect  $\geq 80\%$  of all women to return for the 3-month follow-up.

To determine **acceptability** of the BI, messaging and website, we will calculate Ms for the satisfaction surveys, and inspect responses. We **predict** that the intervention materials will be well-accepted, as shown by mean ratings  $\geq 4$  on a 5-point Likert scale. To further evaluate the **acceptability** of the messaging and website, we will collect use metrics (e.g., timing and frequency of website access, number of clicks on links for information, video view time). We **predict**, and will construe as acceptable, if women receive messages, link to the website, and view videos all the way through/multiple times.

To obtain preliminary evidence of BI **efficacy**, repeated measures ANOVAs will test intervention and time effects on the primary outcomes (alcohol use frequency, quantity, binge frequency; condom use, number of sexual partners; alcohol use before sex). We **hypothesize** an intervention x time interaction for all outcomes; thus, we **hypothesize** that BI recipients but not controls will reduce alcohol use and alcohol use before sex, increase proportion of protected sex, reduce condom use problems and number of partners.

To prepare for a future trial, we also provide preliminary data on mechanisms of action by testing intervention effects on **hypothesized mediators** (e.g., IMB constructs, attitudes, norms, self-efficacy).

**j. Effect sizes and power.** We recognize that effect size estimates based on small samples often have large SDs and wide confidence intervals (CIs). We also acknowledge that we will not have power to detect statistically significant results. Nonetheless, pilot data are useful to gauge whether BI effects are encouraging, to examine distribution of outcome variables, to inform future analytic approaches, and to suggest the range of effect sizes that are reasonable to expect in a future trial. Thus, the focus of our analyses will not be on strict significance testing but on estimating effect sizes and CIs.

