## D. 6. Timeline and Deliverables

**a. Timeline (30 months).** Months (a) 1-3: train staff, get IRB approvals, initiate screening, finalize FG materials; (b) 4-10: recruit 25 women to 6 focus groups, transcribe and analyze data (Aim 1); (c) 10-15: draft BI manual, pilot BI with ~8-15 women, get feedback, revise manual, finalize website (Aim 2); (d) 16-24: recruit 50 women to trial, analyze data (Aim 3); (e) 25-30: prepare and submit manuscripts, plan R01.

**b. Deliverables.** We will achieve these intervention development goals: (a) generate an integrated alcohol and sexual risk reduction BI, tailored to young women and partner type; (b) generate a web-delivered extender that models behavioral skills and maintains motivation; (c) demonstrate feasibility and acceptability of the BI with women in RHFP setting; (d) assess short-term change on target outcomes (i.e., condom use, number of partners, binge drinking, drinks per week); and (e) assess change in hypothesized mediators of change. These achievements will prepare us to submit a R01 to support a fully powered RCT.

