## Data Analyses Plan

For the feasibility data, we produced a Consort flow figure and calculated summary statistics to report the findings. For the acceptability data, we calculated summary statistics and identified illustrative quotes from the semi-structured interviews. Prior to analyzing the efficacy data, we used t-test and chi-square analyses to determine if randomization produced equivalent groups with respect to demographic characteristics and outcome measures.

For the efficacy data, we used inferential statistics to compare the two conditions to one another. Specifically, we used generalized estimating equations (GEE; Hardin & Hilbe, 2013) to examine the impact of the intervention on primary outcomes (i.e., typical drinks per week, maximum drinks per day, number of heavy episodic drinking days, alcohol-related consequences, number of sexual partners, and alcohol use before sex) as well as to model change over time. We used an intent-to-treat approach such that data from all women were used. We hypothesized an intervention-by-time interaction such that participants in the BI, but not the control, condition would reduce alcohol use and sex risk behavior over time. All analyses examined the impact of time (baseline vs. follow-up), intervention condition (control vs. BI), and the time-by-condition interaction controlling for age. When interactions were not significant, models were run without the interaction terms. Count variables (i.e., drinks per week, maximum drinks per day, heavy episodic drinking days, number of partners, drinks before sex) were analyzed using a Poisson distribution unless otherwise indicated. Alcohol consequences were analyzed using linear models.

For condomless sex, a GEE model could not be fit due to significant over-dispersion bounded by a large number of zeroes. Instead, a zero-inflated negative binomial model was chosen based on the (a) lower AIC and BIC values in the negative binomial versus Poisson models, and zero-inflated versus non-inflated models; and the (b) likelihood ratio test comparing zero-inflated Poisson and negative binomial models (lr test:  $\chi^2(1) = 60.76, p < .001$ ) (Long & Freese, 2006). Further, a zero-inflated model is considered particularly appropriate for sexual health research, such as condomless sex (He, Tang, Wang, & Crits-Cristoph, 2014), given that some mechanisms responsible for zero counts in the data differ from

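### The SAP's primary outcomes do not match the protocol's: drinking frequency and the hypothesised condom use problems have no analysis, alcohol-related consequences is made primary without a reason, and condomless sex has no stated status

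*SAP*

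**What the plan says.** Protocol section D.5.i (Data analysis) plans tests of intervention and time effects on the "primary outcomes (alcohol use frequency, quantity, binge frequency; condom use, number of sexual partners; alcohol use before sex", and expects an interaction for every outcome. When it spells this out, it predicts that intervention recipients will drink less, drink less before sex, and "increase proportion of protected sex, reduce condom use problems and number of partners". Condom use problems is not in the parenthetical primary list. It also appears among the potential mediators in D.5.e: "To assess behavioral skills for condom use we will use a measure of condom use problems".

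The deliverables in D.6.b give a shorter set: "assess short-term change on target outcomes (i.e., condom use, number of partners, binge drinking, drinks per week".

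Table 2 has an alcohol row, "Drinks/week, quantity/frequency, maximum quantity", coded as feedback and outcome. It also has a row "Assessment of Correct Condom Use", coded as feedback, outcome and potential mediator or moderator. Both are collected in Aim 3 at baseline and at 3 months.

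The SAP (Data Analyses Plan) applies GEE to the "primary outcomes (i.e., typical drinks per week, maximum drinks per day, number of heavy episodic drinking days, alcohol-related consequences, number of sexual partners" and, last in the list, alcohol use before sex. It then says that GEE could not be fitted for condomless sex and that a zero-inflated negative binomial model was used. It mentions neither a separate drinking-frequency outcome nor condom use problems, and it gives no reason for departing from the protocol's list.

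**The concern.** The protocol does not promise significance. Sections D.5.c and D.5.j promise a pattern of results and a range of effect sizes to support planning of a larger trial. A pattern can be judged only if the reader knows in advance which outcomes make it up. Under the SAP as written, one protocol primary outcome and one explicitly hypothesised outcome are never estimated. Another outcome becomes primary without comment, and the status of a fourth has to be guessed. Because the SAP text post-dates model fitting, it gives a reader no means of telling planned choices from later ones.

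**Working it through.** No formula applies; the check is an item-by-item comparison. The inputs are the list and hypothesis sentence in protocol D.5.i, the measures in Table 2, the intervention targets in D.3.a, and the outcomes that the SAP lists or models.

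**Protocol primary outcomes traced to the SAP**

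| Protocol D.5.i | SAP counterpart | Position |
|---|---|---|
| Quantity | Typical drinks per week; maximum drinks per day | In primary list |
| Binge frequency | Heavy episodic drinking days | In primary list |
| Sexual partners | Number of partners | In primary list |
| Alcohol before sex | Alcohol before sex | In primary list |
| Condom use | Condomless sex (count) | Analysed, status not stated |
| Alcohol use frequency | None of its own | Not analysed separately |

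The tally is 4 + 1 + 1 = 6. Frequency enters only indirectly, through drinks per week and heavy episodic drinking days. The first mixes how often with how much. The second is already the counterpart of binge frequency, which the protocol lists separately.

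**SAP primary outcomes traced back to the protocol**

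Five of the six map to the D.5.i list: the two quantity measures, heavy episodic drinking days, partners, and alcohol before sex. The sixth, alcohol-related consequences, does not (5 + 1 = 6). It is an intervention target in D.3.a, and its instrument (SIP-2R) is coded as an outcome in Table 2. The unexplained step is its rise to primary.

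**The D.5.i hypothesis sentence, five items**

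- Three have a direct SAP analysis: alcohol use, alcohol before sex, and number of partners.
- One changes scale. The protocol hypothesises the proportion of protected sex; the SAP models a count of condomless sex and describes no denominator.
- One, condom use problems, has no analysis. The SAP describes no mediator analysis either, so the measure is not picked up by that route.

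The tally is 3 + 1 + 1 = 5.

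**Timing**

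The SAP is in the past tense. It reports a likelihood-ratio statistic of 60.76 used to choose the condomless-sex model, and it counts re-expressed outliers (3 at baseline, 2 at follow-up). It was therefore written after data were inspected and models fitted.

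**The case against.** The strongest reply is that most of this is labelling in an openly unpowered pilot of 50 women.

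- **Frequency.** It is partly reflected in the drinking outcomes that are modelled. It is absent from the intervention targets in D.3.a and from the deliverables in D.6.b, and all four D.6.b targets are analysed. This limits the consequence, but D.5.i still names frequency as primary alongside quantity and binge frequency, and Table 2 has a measure for it.
- **Consequences.** The outcome is traceable to D.3.a and Table 2. A reader might infer that it is new to the study; it is not. Only its primary label lacks a reason.
- **Condomless sex.** A reader might infer that condom use was dropped. The SAP does not support this: the closed list introduces the GEE models, and condomless sex follows as the outcome GEE could not fit. It is fully analysed and needs only a stated status.
- **Condom use problems.** A reader might call this a dropped primary outcome. It was never in the D.5.i list. It is a hypothesised outcome and a possible mediator, and the protocol's own list and hypothesis are not aligned on it.
- **Quantity.** Representing it by two measures is no defect. Both sit in one Table 2 row, and drinks per week is a named deliverable.

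These replies narrow the point. They do not supply the two missing analyses or the missing explanation.

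**Conclusion.** The point holds as a mismatch that should be corrected. One of six protocol primary outcomes has no stand-alone analysis, one is analysed with its status unstated, one of six SAP primary outcomes is an unexplained addition, and one hypothesised outcome is not analysed. No power or error-rate figure is affected, because the protocol claims none.

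A reader might go further and infer that outcomes were selected on their results. The documents do not support that. They show that the SAP text post-dates fitting, which leaves the order of decisions unknown, but they give no results by outcome. A reader might also infer that the condomless-sex count gives a misleading answer. The documents do not show that either; they show only that a count is not the hypothesised proportion and should not be described as one.

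The verdict rests on two assumptions: that drinking frequency can be derived from the quantity/frequency items in Table 2, and that Assessment of Correct Condom Use is the closest Table 2 measure of condom use problems. The protocol does not state the second, so it needs confirmation.

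**What to change.** 1. Estimate and report alcohol use frequency as a primary outcome, with an effect size and confidence interval.
2. Report condom use problems in the same way, as a hypothesised outcome, after confirming which Table 2 measure carries it. Note its possible mediator role.
3. State that condomless sex is the analysis of the primary outcome condom use. Do not describe a change in the count as a change in the proportion of protected sex.
4. Label alcohol-related consequences as added to the primary list after the protocol, and give the reason.
5. State which outcome and model choices were made after data inspection.

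A short table giving each protocol outcome, its SAP counterpart, its status and the reason for any change would carry items 3 to 5. The cost is SAP wording plus two analyses of measures the protocol says are collected. The downside is two more estimates in an unpowered pilot, to be read as effect sizes with wide intervals rather than as tests.

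### The intent-to-treat statement leaves missing month-3 outcomes unaddressed: women lost to follow-up inform only the baseline mean, which can bias the comparison if loss differs by arm

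*SAP*

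**What the plan says.** On the analysis set, the SAP (Data Analyses Plan) says: "We used an intent-to-treat approach such that data from all women were used". On method, it says that "we used generalized estimating equations (GEE; Hardin & Hilbe, 2013) to examine the impact of the intervention on primary outcomes", and on model terms: "All analyses examined the impact of time (baseline vs. follow-up), intervention condition (control vs. BI), and the time-by-condition interaction controlling for age". Baseline is thus one level of the outcome over time, not a covariate. A non-significant interaction is dropped and the model refitted without it.

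Count outcomes "were analyzed using a Poisson distribution unless otherwise indicated". "Alcohol consequences were analyzed using linear models". For condomless sex, where the GEE could not be fitted, "a zero-inflated negative binomial model was chosen".

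The only group comparison described concerns baseline balance: "we used t-test and chi-square analyses to determine if randomization produced equivalent groups".

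Protocol D.5.i expects at least 80% "of all women to return for the 3-month follow-up". Neither document mentions imputation, weighting, a missing-data assumption, the working correlation, a comparison of lost women with completers, or a sensitivity analysis for loss.

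**The concern.** Intent-to-treat on all women suggests that the randomised comparison is protected against loss to follow-up. Under the models as described, it is not. A woman with no month-3 record supplies a baseline value and nothing else, so each arm's follow-up mean rests on the women who returned. Unweighted GEE is assured in general only when loss is completely random or depends only on model covariates, here condition and age.

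The protocol gives some reason to expect that loss might be selective and might differ by arm. Section A.2 notes limited participation by heavy drinkers in prevention trials, although that concerns taking part and not retention. In Table 1, the BI presents the 3-month visit as a check on the woman's goals, which could deter those who did not change. BI women also receive daily texts for 3 months (D.4.b, D.5.f), while controls receive a fact sheet.

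The stake is the effect estimate. Protocol D.5.j puts estimation of effect sizes and confidence intervals ahead of significance testing, so any bias would be carried into planning the later trial.

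**Working it through.** **Inputs from the documents.** Aim 3 sample of 50 (Protocol D.5.c–d); at least 80% return expected (D.5.i); two time points with condition, time, their interaction and age (SAP). The allocation ratio, actual loss and working correlation are not stated.

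**Rows at the 80% floor.** 50 × 0.80 = 40 return and 10 do not. The model then has 50 + 40 = 90 of 100 possible rows, or about 20 follow-up rows per arm if allocation and loss are even. With full retention, no row is missing.

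**What independence GEE estimates.** Leaving age aside, the fitted ratio of ratios is

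[mean(Y2 of BI returners) / mean(Y1 of all BI)] ÷ [mean(Y2 of control returners) / mean(Y1 of all controls)].

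Let s = mean(Y2 of returners) / mean(Y2 of all) in an arm. The estimate is then the true ratio × s(BI) / s(control). If selection is the same in both arms, the factors nearly cancel in the interaction, but each arm's time ratio is still multiplied by its own s.

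Under an exchangeable structure, a lost woman's baseline deviation helps correct the follow-up mean. Loss explained by baseline is then largely recovered: essentially exactly for the linear model, approximately for Poisson. Loss that depends on the unseen month-3 value is not.

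**Simulated size.** All settings below are assumptions, not figures from the documents. Samples were large, to isolate bias, with loss averaging about 20% and a log-odds slope of about 1 per SD (0.7–1.0 in setting A).

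- A: gamma-Poisson counts, mean 10, dispersion 0.8, within-woman correlation 0.7, true ratio 1.0.
- B: Poisson with log-normal heterogeneity, mean 8, log SD 0.7, latent correlation 0.6, true ratio 0.80.
- C: latent correlation 0.7, true ratio 1.0.
- D: count distribution as in A, latent correlation 0.8, true ratio 1.0, one run per pattern.

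| Loss depends on | Setting | True | Independence | Exchangeable |
|---|---|---|---|---|
| Baseline, one arm only | A | 1.0 | 0.903 | 0.985 |
| Baseline, opposite directions by arm | A | 1.0 | 0.872 | 0.983 |
| Baseline, 28% v 12% loss | A | 1.0 | 0.927 | 0.982 |
| Baseline, BI arm only | B | 0.80 | 0.754 | 0.802 |
| Baseline, BI arm only | C | 1.0 | 0.89 | 0.98 |
| Baseline, selective loss | D | 1.0 | 0.80–0.86 | 0.95–0.97 |
| Baseline, same in both arms | B | 0.80 | 0.810 | 0.805 |
| Month-3 value, BI arm only | B | 0.80 | 0.673 | 0.695 |
| Month-3 value, same in both arms | B | 0.80 | 0.816 | 0.818 |

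Random loss in B gave 0.791 and 0.801, so differences of about 1% are noise.

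**Shifts when baseline-driven loss differs by arm.**
- Independence: A, 1 − 0.903 = 10%, 1 − 0.872 = 13%, 1 − 0.927 = 7%; B, 1 − 0.754/0.80 = 6%; C, 11%; D, 14–20%.
- Exchangeable: about 2% in A and C, nil in B, 3–5% in D.
- Conditioning on baseline within arm: 0.994–0.997 in A and 0.99 in C, a shift of 1% or less.

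**Shifts when month-3 drinking drives loss in the BI arm.** B: 1 − 0.673/0.80 = 16% (independence) and 1 − 0.695/0.80 = 13% (exchangeable). C: 0.82–0.87 under every method tried, including conditioning on baseline, or 13–18%.

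**Time effect when loss is the same in both arms (B).** The control time ratio, truly 1, was 0.924 / 0.975 (independence / exchangeable) for baseline-driven loss and 0.842 / 0.875 for month-3-driven loss. The BI arm's time ratio is the control ratio times the interaction: 0.924 × 0.810 = 0.748 against 0.80, a 6% fall. So both arms drift the same way, and a model without the interaction would read that drift as change over time.

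**Linear outcome (B; mean 10, SD 6, true interaction −2.0).** Baseline-driven loss in BI only: −2.70 (independence), −2.00 (exchangeable). Month-3-driven in BI only: −3.01 and −2.61.

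**The case against.** The strongest reply is that the documents show an unstated assumption, not a demonstrated bias. With an exchangeable structure, loss that depends on baseline drinking costs little, and the SAP may have used one. The bias in the interaction also needs selection to differ by arm. Both points stand. A reader might infer that the models are unbiased only if loss is unrelated to drinking or risk; the results above do not support that.

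A reader might also infer that the condomless-sex model treated repeated rows as independent and so carries the same bias figures. The SAP does not say how its repeated rows or missing follow-up were handled, and no zero-inflated model was fitted here, so no figure is given for it.

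The protocol limits loss: remote follow-up (D.5.h), reminders, two locators and payment for follow-up in both arms (D.1.d), and exclusion of women planning to move (D.1.c). The SAP reports a CONSORT figure. These measures may reduce loss, but they do not make it random, and none compares lost women with those who returned.

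Sampling error at this size is larger than most of these shifts. With 25 per arm and an assumed SD of the log interaction of 0.24–0.31, the 95% limits span a factor of exp(1.96 × 0.24) = 1.6 to exp(1.96 × 0.31) = 1.8 either way. The protocol already says that the pilot is unpowered and its intervals wide. That limits the consequence, but the interval does not reveal a bias in its centre.

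Finally, imputing skewed, zero-heavy counts from about 20 returners per arm is fragile. That is a reason to add imputation beside the GEE, not to replace it.

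**Conclusion.** The point holds in a conditional form. The sentence on all women is literally compatible with the model, but it does not deal with missing month-3 outcomes. That a lost woman adds only her baseline row is inferred from the absence of any stated imputation or weighting.

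If baseline drinking drives loss differently by arm, the interaction ratio is off by roughly 10–20% in most settings under independence (6–7% in the mildest), and by about 2–5% under exchangeable (nil in one setting). If the dependence is the same in both arms, the interaction is little affected but the time effect is biased; that matters because the SAP drops non-significant interactions, which are likely to be common in an unpowered pilot. Loss tied to month-3 drinking in one arm biases the interaction under any working correlation.

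These sizes rest on assumed loss of about 20%, a log-odds slope of about 1 per SD and within-woman correlation of 0.6–0.8. Actual loss is not in the documents, so they do not show that the trial's estimates were in fact biased.

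**What to change.** - Keep the GEE, and state an exchangeable working correlation.
- Add an analysis of all randomised women with month-3 outcomes multiply imputed within arm from the baseline outcome and age, for the GEE outcomes and for condomless sex. State how the zero-inflated model handles repeated rows.
- Add one sensitivity analysis for loss related to month-3 behaviour, for example setting the follow-up value of lost BI women to their baseline value. Imputation from baseline cannot address that kind of loss. This is a single chosen departure and not a bound.
- Report the number lost per arm, and compare lost women with completers by arm on baseline drinking and number of partners.
- Reword the intent-to-treat sentence to say that all randomised women contribute their available data, and state the missing-data assumption.

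The cost is SAP wording and modest programming on data already held, with possibly slightly wider intervals. In simulation at 25 per arm the loss of precision was negligible (SD of the log interaction about 0.30 versus 0.31). If the CONSORT figure shows full retention, only the rewording is needed.
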